7.4. End of Study and Commercial Availability

Each patient will complete an End of Study visit that should occur within 30 days after bardoxolone methyl becomes available to the patient through commercial channels. Commercial availability is defined as when the commercial drug is approved for use by the relevant regulatory authority and is made available through commercial channels to that patient. The timing of commercial availability can vary by country, site and/or patient, depending on these factors. The scheduled study visits and IP dispensation will continue for each patient until commercial availability or alternative drug supply arrangements are made. More information on other scenarios for study closure are included in Section 7.5.

7.5. Criteria for Study Termination

The Sponsor reserves the right to discontinue the study at any time for clinical or administrative reasons, or if required by regulatory agencies. If the Sponsor discontinues the study, all study drug will be discontinued and the investigator will be responsible for securing any alternative therapy to be administered, as appropriate.

7.6. Criteria for Premature Termination or Suspension of Investigational Sites

A study site may be terminated prematurely or suspended if the site (including the investigator) is found in significant violation of good clinical practice (GCP), protocol, or contractual agreement with Sponsor or the site is unable to ensure adequate performance of the study.

7.7. Procedures for Premature Termination or Suspension of the Study or the Participation of Investigational Sites

In the event that the Sponsor, an Institutional Review Board (IRB)/Independent Ethics Committee (IEC), or regulatory authority elects to terminate or suspend the study or the

participation of an investigational site, a study-specific procedure for early termination or suspension will be provided by the Sponsor.

7.8. Schedule of Assessments

[Table 5](#) lists the overall schedule of assessments for the study.

Table 5: Schedule of Assessments

Assessment	Study Week (Day±Days)	Screening Visit ^a	Day 1 ^{a,c}	Week 1 (Phone) Day 3 ± 2 Days	Week 1 Day 7 ± 3 Days	Week 2 (Phone) Day 10 ± 2 Days	Week 2 Day 14 ± 3 Days	Week 3 (Phone) Day 21 ± 2 Days	Week 4 Day 28 ± 3 Days	Week 4 (Phone) Day 31 ± 2 Days	Week 5 (Phone) Day 38 ± 2 Days	Week 6 Day 42 ± 3 Days	Week 7 (Phone) Day 45 ± 2 Days	Week 8 Day 56 ± 3 Days	Week 12 Day 84 ± 3 Days	Week 24 ± 3 Days, Every 24 Weeks ± 3 Days	End of Study Visit ^b
Informed consent		X ^c	X ^c														
Inclusion/Exclusion		X	X														
Demographics ^d		X	X														
Prior and Concomitant medications		X	X	X	X	X	X	X	X	X	X	X	X	X	X	X	X
Medical History		X	X														
Height		X	X		X		X		X			X		X	X	X	X
Weight at home			X	X	X	X	X	X	X	X	X	X	X	X	X	X	
Weight in-clinic		X	X		X		X		X			X		X	X	X	X
Dispense Weight & Study Drug Diary			X				X		X			X		X	X	X	
Collect/Review Weight & Study Drug Diary				X	X	X	X	X	X	X	X	X	X	X	X	X	X
Vital sign measurements		X	X		X		X		X			X		X	X	X	X
Physical examination		X	X		X		X		X			X		X	X	X ^e	X ^e
Pregnancy test ^f			X													X	
Dispense study drug			X				X		X			X		X	X	X	
Collect study drug							X		X			X		X	X	X	X
Telephone contact				X		X		X		X	X		X				
Adverse event collection			X	X	X	X	X	X	X	X	X	X	X	X	X	X	X
Basic Lipid Panel			X													X	X
Clinical Chemistries (incl. eGFR) ^g		X	X		X		X		X			X		X	X	X	X
BNP and NT-Pro BNP		X	X		X		X		X			X		X	X	X	X
Hematology		X	X		X		X		X			X		X	X	X	X
Urine collection for ACR ^h		X	X						X					X	X	X	X
Tanner Staging ⁱ			X													X	X

Abbreviations: AE=adverse event; BNP=B-type natriuretic peptide; eGFR=estimated glomerular filtration rate; NT-proBNP=N-terminal prohormone B-type natriuretic peptide; ACR=albumin to creatinine ratio; WOCBP=women of child-bearing potential

^a A screening visit will be conducted for subjects whose planned EAGLE Day 1 visit is not within 8 weeks of the eligibility lab assessments from the prior qualifying study. Refer to Section 7.1 for additional details. Subjects requiring a screening visit will be consented prior to the start of any screening assessments. All other subjects will be consented at the start of the Day 1 visit, before any procedures are performed for this, or the prior study.

^b After the Week 24 visit, subjects will continue to be assessed in person every 24 weeks until the study ends. The End -of- Study visit should occur within 30 days after bardoxolone methyl becomes available to the subject through commercial channels. For additional details, see Section 7.4. Subjects who will be discontinued from the study prior to commercial availability of bardoxolone methyl must also complete all End-of-Study assessments as soon as possible (if possible, within 30 days of discontinuation).

^c On Day 1, all procedures should be performed before study drug administration. AE assessment on Day 1 should be performed following study drug administration. If the Day 1 visit for EAGLE is the same as the end-of-study visit for CARDINAL (all versions) or FALCON (protocol version 5 and older), the laboratory assessments required for both visits should only be completed once.

If the Day 1 visit for EAGLE is the same as the end-of-study visit for FALCON (protocol version 6 and newer), the lab assessments required for both visits should be completed for each study individually.

^d Demographics are to be performed on the earliest study visit, whether it be Day 1 or a Screening visit, if necessary.

^e Assessment should include a complete physical examination as described in Section 9.9.7.

^f A serum pregnancy test will be performed at any point in time if a pregnancy is suspected. All other pregnancy assessments will be urine pregnancy tests. Additional pregnancy assessments will be performed more frequently if required by local law or requested by local health authorities or IRBs/IECs.

^g eGFR will not be calculated by the central lab.

^h Urine albumin to creatinine ratio will be measured by first morning void spot urine collection. Appropriate containers for the collection will be provided to the subject at the visit prior to collection.

ⁱ Adolescent patients from the FALCON (402-C-1808) ($12 \leq \text{age} < 18$ years at consent) will be assessed by Tanner staging at all specified timepoints.

8. SELECTION AND WITHDRAWAL OF PATIENTS

8.1. Patient Inclusion Criteria

Diagnosis and main criteria for inclusion:

1. Patients who are participating (or who have participated) in qualifying studies and who have not been required to discontinue study treatment for protocol or safety reasons and who have completed required End-of-Treatment and/or Follow-up visits in a prior clinical study with bardoxolone methyl and who, according to the assessment of the investigator, have a potential positive benefit-risk assessment for participating in the trial;
2. Meets the following eligibility criteria based on assessments from the prior qualifying study or from a screening visit, if applicable.
 - a. Not expected to reach ESKD or nephrotic syndrome within 12 weeks of study enrollment, in the investigator's judgement; subjects with $eGFR < 20 \text{ ml/min/1.73m}^2$ should be discussed with the medical monitor before enrollment (eg, such subjects with an average rate of $eGFR$ decline $> 1.0 \text{ ml/min/1.73m}^2$ per month in the 3 months prior to eligibility assessment may not be eligible);
 - b. $BNP < 200 \text{ pg/mL}$ at the last on-treatment visit in the prior qualifying study or at a screening visit, if applicable, as shown in Section 7.1 and Table 5;
 - c. No occurrence of a cardiovascular serious adverse event in the prior qualifying study or in the interval between the end of the qualifying study and the screening visit, if applicable.
3. Willing and able to comply with scheduled visits, treatment plan, laboratory tests, and other study procedures;
4. Evidence of a personally signed and dated informed consent document (and assent form if necessary) indicating that the patient (or a legally acceptable representative) has been informed of all pertinent aspects of the study prior to initiation of any protocol-mandated procedures.

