7. INVESTIGATIONAL PLAN

7.1. Overall Study Design

This extended access study will assess the long-term safety and tolerability of bardoxolone methyl in qualified patients with CKD who previously participated in a qualifying clinical study with bardoxolone methyl. The CARDINAL study (402-C-1603, NCT03019185, EudraCT 2016-004395-22) and FALCON study (402-C-1808, NCT03918447, EudraCT 2018-004651-20) are the only qualifying clinical studies at this time.

The Day 1 visit of EAGLE is not required to occur on the same day as the End of Study visit of the prior qualifying study. Lab assessments from the qualifying study may be used for EAGLE eligibility and maximum treatment dose assignment (Week 100 for CARDINAL or FALCON protocol versions 1.0 through 5.0, and Week 108 [B] for FALCON protocol versions 6.0 and newer) if those assessments were done ≤ 8 weeks before Day 1. In the event the eligibility lab assessments were obtained > 8 weeks before the planned Day 1 EAGLE visit, a screening visit will be required for EAGLE enrollment.

Table 4 clarifies potential situations with patient eligibility.

Table 4: Lab Assessments for Eligibility

[figure not shown]
Patients Enrolling from CARDINAL or FALCON	
Day 1 of EAGLE Study	Lab Assessments for Eligibility
Day 1 is equal to end-of-study visit from the prior qualifying study	Week 100 for CARDINAL or FALCON protocol versions 1.0 through 5.0 Week 108 (B) for FALCON versions 6.0 and newer
Day 1 is ≤ 8 weeks after the eligibility lab assessments from the prior qualifying study	Week 100 for CARDINAL or FALCON protocol versions 1.0 through 5.0 Week 108 (B) for FALCON versions 6.0 and newer
Day 1 is > 8 weeks after the eligibility lab assessments from the prior qualifying study	A screening visit is required, and these lab assessments will be used for eligibility

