8.3. Screening Period

The Day 1 visit of EAGLE is not required to be the same day as the End of Study visit of the prior qualifying study. As shown in [Table 4](#), lab assessments from the qualifying study may be used for EAGLE eligibility and maximum treatment dose assignment (Week 100 for CARDINAL or FALCON protocol versions 1.0 through 5.0, and Week 108 [B] for FALCON versions 6.0 and newer) if those assessments were done ≤ 8 weeks before Day 1. In the event the eligibility lab assessments were obtained > 8 weeks before the planned EAGLE Day 1 visit, a screening visit will be required for EAGLE enrollment.

Patients who previously were ineligible due to previous eGFR requirements may be rescreened once.

The maximum bardoxolone methyl dose will be determined by proteinuria status based on the ACR value from the eligibility lab assessments from the prior qualifying study, or for patients requiring a screening visit, the maximum bardoxolone methyl dose will be determined based on the ACR values from the screening labs.

Subjects requiring a screening visit will be consented prior to the start of any screening assessments. All other subjects will be consented at the start of the Day 1 visit, before any procedures are performed for this, or the prior study.

All screening procedures should be completed per the schedule of assessments in [Table 5](#).

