11.6. Recording Adverse Events

All conditions present prior to the administration of the first dose of study drug (Day 1) should be documented as adverse events in the prior trial with bardoxolone methyl. Any new event/condition that starts during the gap between prior qualifying study and Day 1 of EAGLE should be recorded as medical history in EAGLE. AEs should be reported from the time of the first dose through 30 days after the last dose or the End of Study visit, whichever is earlier.

Information to be collected includes type of event, date of onset, date of resolution, investigator-specified assessment of severity and relationship to study drug, seriousness, as well as any action taken.

For guidance on how to handle AEs that change in severity (eg, worsening or improving) see the eCRF Completion Guidelines. All drug-related (possibly, probably, or definitely related, see Section 11.4) AEs and clinically significant abnormal laboratory test results reported or observed during the study must be followed to resolution (either return to baseline, within normal limits, or stabilization). All non-drug related AEs or clinically significant abnormal laboratory results will be followed through the 30 days after the last dose of study drug.

AEs resulting from concurrent illnesses, reactions to concurrent illnesses, reactions to concurrent medications, or progression of disease states must also be reported. Preexisting conditions (present before the start of the AE collection period) are considered concurrent medical conditions and should NOT be recorded as AEs. However, if the patient experiences a worsening or complication of such a concurrent condition, the worsening or complication should be recorded as an AE. Investigators should ensure that the AE term recorded captures the change in the condition (eg, “worsening of...”). Any improvement in condition should be documented per Section 9.9.7.

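### Inclusion criterion 2c ends its cardiovascular SAE check at the screening visit, not at Day 1, so the stretch just before first dose is left to investigator judgement alone

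*Protocol*

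**What the plan says.** Protocol 8.1 opens criterion 2 by naming its data sources: "Meets the following eligibility criteria based on assessments from the prior qualifying study or from a screening visit, if applicable". Item 2c then rules out a cardiovascular SAE in the parent study or "in the interval between the end of the qualifying study and the screening visit, if applicable". The synopsis and the SAP's technical summary carry the same wording.

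A delay between the studies is allowed. Section 8.3 states: "The Day 1 visit of EAGLE is not required to be the same day as the End of Study visit". Parent-study labs may serve for eligibility "if those assessments were done ≤ 8 weeks before Day 1". The lab visit is "Week 100 for CARDINAL or FALCON protocol versions 1.0 through 5.0", and Week 108 (B) for later FALCON versions. Table 4 in Section 7.1 has a row for entry without screening, "Day 1 is ≤ 8 weeks after the eligibility lab assessments from the prior qualifying study". For older labs it says: "A screening visit is required, and these lab assessments will be used for eligibility".

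For recording events, Section 11.6 uses a different end point: "Any new event/condition that starts during the gap between prior qualifying study and Day 1 of EAGLE should be recorded as medical history in EAGLE". Section 9.9.19 likewise sends between-study events to the medical history form when enrolment is delayed. Table 5 marks both Inclusion/Exclusion and Medical History at Day 1.

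**The concern.** Criterion 2c takes cardiovascular SAEs out of the investigator's discretion: one such event in the parent study is disqualifying. As worded, it disqualifies for an event up to about two years old but is silent on one in the days before the first EAGLE dose.

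The protocol's own risk account makes that stretch relevant. Section 5.1.2.1 reports more fluid overload and heart failure admissions in BEACON, places the excess in roughly the opening three to four weeks of treatment, and lists an earlier heart failure admission among the risk factors. Patients who took placebo in the parent study first receive the drug in EAGLE.

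Delayed entry is foreseen. Appendix 1, Section 4 tells sites to consider postponing enrolment, and SAP 10.1 has a category for delayed rollover.

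A patient with such an event who is enrolled has met 2c as written. The event would therefore not put the patient among the entry-criteria deviations of SAP 7.3 or in the eligibility listing of SAP 7.5.

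**Working it through.** The study is descriptive and gives no sample size or power figure, so there is no plan figure to reproduce. The check is of the wording, plus date arithmetic.

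**Step 1. Where 2c stops, by route of entry**

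| Route | Covered by 2c | Not covered |
|---|---|---|
| Day 1 is the parent end-of-study visit | Parent study | Nothing |
| Delayed Day 1, parent labs at most 8 weeks old, no screening visit | Parent study | Parent end of study to Day 1 |
| Screening visit held | Parent study, and its end to screening | Screening to Day 1 |

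In the second row the interval clause has no end point, because the only one it names is a visit that does not take place.

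**Step 2. Length of the gap without a screening visit**

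Let L be the week of the eligibility labs and E the week of the parent end of study. The latest Day 1 is L + 8, so the longest uncovered stretch is (L + 8) − E.

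- CARDINAL: L = 100 (8.3). E = 104, stated only in the Version 3 change log and used here for timing only. (100 + 8) − 104 = 4 weeks, or 28 days.
- FALCON versions 1 to 5: L = 100, E not stated. If E = 104 (assumption), 4 weeks. For E from 100 to 108, the range is 8 to 0 weeks.
- FALCON version 6 and newer: L = 108, E not stated. (108 + 8) − E = 116 − E. For E from 108 to 116, the range is 8 to 0 weeks; E = 112 (assumption) would give 4.

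**Step 3. Length of the gap after a screening visit**

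Table 5 gives no window from screening to Day 1. The 8-week limit in 7.1, 8.3 and Table 5 note a is worded for parent-study labs. The note under Protocol Figure 1 refers to the last lab assessments being more than 8 weeks old, which could be read as covering screening labs too. The matching note in the SAP says 4 weeks, while SAP 7.2 and SAP Table 1 note a say 8. The documents therefore do not settle this length.

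**Step 4. Other criteria that might catch the event**

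- Day 1 re-check of Inclusion/Exclusion (Table 5, 9.9.2): applies the same 2c wording.
- Criterion 2b (BNP): uses the last on-treatment or screening value. BNP is drawn on Day 1 but is not the eligibility value.
- Exclusion 2: only SAEs that are from a clinical study, still ongoing, and judged related to bardoxolone.
- Inclusion 1 (benefit-risk) and Exclusion 5 (unsuitability): investigator judgement, not specific to cardiovascular events.
- Sections 9.9.19 and 11.6: record the event, with no link to eligibility.

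No cardiovascular-specific rule covers the stretches found in Step 1.

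**The case against.** The strongest reply is that the patient does not simply walk in. Inclusion 1 requires a potentially favourable benefit-risk assessment by the investigator, which is a positive condition of entry. Exclusion 5 bars anyone the investigator finds unsuitable. Medical history, vital signs and physical examination are done on Day 1 before dosing, and 9.9.2 directs eligibility questions to the medical monitor. This stands. A reader might infer that a patient with a recent cardiac SAE must be accepted; the documents do not support that. They support only that 2c does not bar the patient.

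A reader might also infer three further things:

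- *That the wait after screening is unlimited.* No limit is clearly stated, but the Figure 1 notes can be read as setting one, so this cannot be asserted.
- *That the adverse event tables are distorted.* They are not. An event starting after first dose is treatment-emergent for every patient, and the earlier event remains visible in medical history.
- *That the BEACON risk carries over unchanged.* Section 5.1.2.1 ties it to Stage 4 CKD with type 2 diabetes and says it was not seen in six earlier CKD studies, mostly in Stage 3b. EAGLE takes patients from the Alport and ADPKD trials, and Section 9.1.1 adds close monitoring after dosing. This weakens the likely consequence but does not close the gap.

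The phrase about applicability in 2c could be read loosely, as reaching any time between the studies. The text names only the screening visit as an end point, so a site is not bound to that reading.

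Finally, SAP Section 2 reports that development was discontinued and that sites were told on 10 May 2023. An amendment may therefore have little effect on enrolment. That limits the practical value of the change, not the accuracy of the point.

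**Conclusion.** The point holds as a gap in a stated safety criterion. Criterion 2c does not reach Day 1 on either delayed route, and no other cardiovascular-specific criterion fills the space. Without a screening visit the gap is up to about 4 weeks for CARDINAL, provided end of study is Week 104. For FALCON it lies between 0 and 8 weeks, because the end-of-study week is not given. With a screening visit the gap runs from screening to Day 1, and the documents do not fix its length.

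It does not arise when Day 1 is the parent end-of-study visit. The documents do not say how many patients fall in the gap. No statistical result changes. What remains is a mismatch between the end point in 2c (screening) and the one in 11.6 (Day 1): the protocol collects the event but does not use it for eligibility.

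**What to change.** Reconcile 2c with the gap described in 11.6 so that the cardiovascular SAE interval runs from the end of the parent study to Day 1, whether or not there is a screening visit. The criterion 2 stem should admit the Day 1 medical history as a data source for 2c. Make the change in Protocol 8.1, the synopsis and the SAP's technical summary.

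The cost is a wording amendment. Inclusion/Exclusion and Medical History are already reviewed on Day 1, so no procedure is added. The downside is that a few patients with a recent cardiovascular SAE would no longer enter. If enrolment has already closed, between-study events already recorded as medical history could be identified for the study report instead.

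Separately, ask the sponsor to reconcile Table 4, Section 8.3, Table 5 note a and the two Figure 1 notes (8 weeks in the protocol, 4 weeks in the SAP) on how old screening labs may be at Day 1. Which limit applies is for the sponsor to settle.

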8.2. Patient Exclusion Criteria

All patients with any of the following conditions or characteristics must be excluded from the study:

1. Participation in other investigational clinical studies involving interventional products being tested or used in a way different from the approved form or when used for an unapproved indication;
2. Patients who have an ongoing SAE from a clinical study that is assessed by the investigator as related to bardoxolone methyl;
3. Unwilling to practice acceptable methods of birth control (both males who have partners of childbearing potential and females of childbearing potential) while screening, taking study drug, and 30 days after last study drug dose;
4. Women who are pregnant or breastfeeding;
5. Patient is, in the opinion of the investigator, unable to comply with the requirements of the study protocol or is unsuitable for the study for any reason;
6. Known hypersensitivity to any component of the study drug.

8.3. Screening Period

The Day 1 visit of EAGLE is not required to be the same day as the End of Study visit of the prior qualifying study. As shown in [Table 4](#), lab assessments from the qualifying study may be used for EAGLE eligibility and maximum treatment dose assignment (Week 100 for CARDINAL or FALCON protocol versions 1.0 through 5.0, and Week 108 [B] for FALCON versions 6.0 and newer) if those assessments were done ≤ 8 weeks before Day 1. In the event the eligibility lab assessments were obtained > 8 weeks before the planned EAGLE Day 1 visit, a screening visit will be required for EAGLE enrollment.

Patients who previously were ineligible due to previous eGFR requirements may be rescreened once.

The maximum bardoxolone methyl dose will be determined by proteinuria status based on the ACR value from the eligibility lab assessments from the prior qualifying study, or for patients requiring a screening visit, the maximum bardoxolone methyl dose will be determined based on the ACR values from the screening labs.

Subjects requiring a screening visit will be consented prior to the start of any screening assessments. All other subjects will be consented at the start of the Day 1 visit, before any procedures are performed for this, or the prior study.

All screening procedures should be completed per the schedule of assessments in [Table 5](#).

